6.2 SUBJECT ENROLLMENT

It is the responsibility of the investigator to ensure that subjects are eligible to participate in the study prior to enrollment and throughout the study. Documentation of the personally signed and dated informed consent of each subject, using the study-specific ICF, is required before initiating the Screening process. After written informed consent has been obtained and eligibility to participate established, investigative site personnel will obtain the subject's identification number. Only eligible subjects will be allocated to the open label FCA 1 mg/0.1mL or 2mg/0.1 mL.

Enrollment will occur in two parts in order to minimise the likelihood that subjects will be exposed to risks. During part 1 & 2, subjects will be screened one by one as only one patient will initially be enrolled during part 1 of the trial. The first enrolled subject will participate in a screening period of up to 14 days and a follow-up period of 28 days, to detect an IOP response.

After first subject has completed the follow-up of 28 days after FCA 1mg/0.1 mL injection, The subject's safety data will be reviewed the safety data of this will be reviewed by an independent safety review committee to determine whether to commence enrolment of additional 2 patients in the first cohort of 1mg/0.1mL dose of FCA. Enrolment will be stopped if >2 patients experience limiting-toxicity adverse event related to the study drug. If no more than two adverse events considered to be related to the study drug occur with limiting toxicity, the second cohort will be recruited. Dose-limiting toxicity is defined by intraocular inflammation, elevated IOP, reduced vision (loss of ≥ 15 letters), or haemorrhage within 28 days after injection.

Part 2 will take in place if the 3 subjects have tolerated well the dose. Part 2 initially involves a single subject treated with 2mg/0.1mL FCA to assess safety and tolerability. This subject will be followed for up to 28 days and reviewed by an independent safety

review committee prior to the recruitment of a further 5 subjects treated with 2mg/0.1mL FCA totalling in 6 subjects in the second cohort.

Meeting minutes will be generated at each meeting and included in the sponsor's study files. Formal reports will not be prepared prior to or following these meetings. As general guidance, a subject will be considered to have tolerated a dose if the subject experiences no clinically significant drug-related adverse event or laboratory abnormality. Conversely, a subject will not be considered to have tolerated the dose if he experiences a clinically significant drug-related adverse event or laboratory abnormality during the study drug administration or post-administration follow-up period.

Safety to cataract will be reviewed among all participants at the 150 day review.

It is understood that safety is a medical judgment that cannot be prospectively defined in detail. Subjects will be closely monitored with clinical observations and safety laboratory testing.

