1.1 SYNOPSIS

Title:	A Phase 1b, study of safety and tolerability of Intravitreal Fludrocortisone acetate (FCA in Patients with Geographic Atrophy (GA)
Sponsor:	Eye Co Pty Ltd
Protocol Number, Version and Date:	EC-FCA-001/ Version 1.3 / 22 January 2020
Investigational Product, Dose and Route of Administration:	Fludrocortisone acetate (FCA) 1mg/0.1ml & 2mg/0.1ml Intravitreal (IVT) injection
Rationale for dose:	
Single dose of 0.1 ml in a concentration of 1mg/0.1 mL and 2mg/0.1mL was selected based on previous pre-clinical model (Kivilcim et al). There were no signs of retinal toxicity on slit-lamp examination, indirect ophthalmoscopy, or by light microscopy in all eyes injected with 400µg/0.1mL, 1mg/0.1mL and 2mg/0.1mL. However, it was reported 1 case of intravitreal haemorrhage in 4 mg/0.1 mL.
 
Systemic injection of Fludrocortisone acetate has serious mineral corticoid and glucocorticoid side effects such as hypertension, potassium loss, Cushingoid changes, etc. Intravitreal injection fludrocortisone acetate may avoid systemic side effects.

Objectives:	To determine safety and tolerability of a single dose intravitreal (IVT) injection of 1mg/0.1mL and 2mg/0.1mL FCA in subjects

with GA secondary to Age-Related Macular Degeneration (AMD).

Study Population: Study population will comprise of patients with GA secondary to AMD in both eyes with no previous treatment. The study is planned to enrol up to 9 participants.

Study Design: This study is planned to enrol 9 participants to assess dose escalation based on a 3+3 algorithm. Enrolment will stop if > 2 patients experience dose-limiting toxicity at any time during the study. Dose-limiting toxicity is defined by intraocular inflammation, elevated IOP, reduced vision (loss of ≥ 15 letters), or haemorrhage within 28 days after injection.

Part 1 involves a single participant to assess safety and tolerability of 1mg/0.1mL FCA. This participant will be followed for up to 28 days and reviewed by a safety review committee prior to the recruitment of a further 2 participants treated with 1mg/0.1mL FCA totalling in 3 participants in the first cohort.

Part 2 involves a single participant to assess safety and tolerability of 2mg/0.1mL FCA. This participant will be followed for up to 28 days and reviewed by an independent safety review committee prior to the recruitment of a further 5 participants treated with 2mg/0.1mL FCA totalling in 6 participants in the second cohort.

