5.2 TREATMENTS ADMINISTERED

5.2.1 DOSE LEVELS AND STUDY ARMS

A single dose of 1- and 2 mg Fludrocortisone acetate/0.1mL will be tested in this study. Subjects will receive 1 IVT injection as outlined in the table below.

	Treatment Arm	Dose Escalation
Part 1	Fludrocortisone acetate 1 mg/0.1mL at Day 0	If no dose limiting toxicity is observed in 3 patients at this given dose level, the dose will be escalated to the following level:
Part 2	Fludrocortisone acetate 2 mg/0.1mL at Day 0	

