6 STUDY PROCEDURES

6.1 STUDY DESIGN

This is a Phase 1b study to assess the safety and tolerability of a single dose of IVT injection of Fludrocortisone acetate in subjects with GA associated with Age-Related Macular Degeneration.

Patients diagnosed with GA associated with age-related macular degeneration in the study eye and who meet all inclusion/exclusion criteria will be included in the study.

The study is planned to enroll an initial cohort of 3 patients in a dose of 1mg/0.1mL. A total of 9 participants can be included to assess dose escalation based on 3+3 algorithm.

Patients should be screened up to 14 days before receiving Fludrocortisone acetate. Upon entry into the study, patients will be assigned a subject screening number. Subjects who meet all inclusion and exclusion criteria and are confirmed as eligible by the CRC will return to the clinic for the administration of single dose IVT Fludrocortisone acetate (Day 0) as outlined in Section 7.1.

All subjects will return to the clinical site on Day 1 and Day 7 to assess acute safety after the injection. After that, all subjects will return for another 6 follow-up visits and 6 months after the injection. See Study Outline below.

Safety will be assessed throughout the study; serial blood samples and urine samples will be collected. Blood samples will also be collected for the PK assessment of Fludrocortisone acetate.

The planned length of participation in the study for each subject is approximately 6 months (from Day 0 – through completion of the Month 6 (Day 150) follow-up procedures).

The study is planned to take place over approximately 12 months (from screening of the first subject through completion of the last subject's exit visit).

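### One sentence in Section 6.2 opens the 2 mg cohort with up to two related dose-limiting events at 1 mg, against Section 5.2.1, the next paragraph of 6.2 and, after 2 of 3, the named 3+3 method

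*Protocol*

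**What the plan says.** Four texts in the protocol bear on moving from 1 mg to 2 mg.

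- **Section 5.2.1**, dose escalation column: "If no dose limiting toxicity is observed in 3 patients at this given dose level, the dose will be escalated".
- **Section 6.2, second-cohort sentence**: if "no more than two adverse events considered to be related to the study drug occur with limiting toxicity, the second cohort will be recruited". The same section identifies that cohort: "2mg/0.1mL FCA totalling in 6 subjects in the second cohort".
- **Section 6.2, next paragraph**: "Part 2 will take in place if the 3 subjects have tolerated well the dose". The guidance that follows says "a subject will be considered to have tolerated a dose if the subject experiences no clinically significant drug-related adverse event or laboratory abnormality".
- **The halt**: Section 6.2 has "Enrolment will be stopped if >2 patients experience limiting-toxicity adverse event related to the study drug"; Section 1.1 has "Enrolment will stop if > 2 patients experience dose-limiting toxicity at any time during the study", with no relatedness condition.

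On the design, Section 6.1 states: "A total of 9 participants can be included to assess dose escalation based on 3+3 algorithm". Sections 1.1 and 6.2 lay out 3 participants at 1 mg and 6 at 2 mg. Section 8.6 allows up to 12 and also refers to 3+3. A DLT is intraocular inflammation, elevated IOP, a loss of 15 or more letters, or haemorrhage, within 28 days of injection. That definition does not mention relatedness.

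**The concern.** One related DLT among the three 1 mg participants is enough to produce opposite instructions. Section 5.2.1 and the Part 2 sentence hold the dose; the second-cohort sentence recruits at twice the dose. The second-cohort sentence cannot mean completing the 1 mg group, because the section itself says that the second cohort is the 2 mg group.

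Section 2.3.3 states that the drug has not been given intravitreally to humans, and Section 4 selects the better-seeing eye when both qualify. Followed literally, the sentence would expose further participants to 2 mg after two of three had a related DLT at 1 mg, which can mean a loss of 15 or more letters.

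**Working it through.** **Step 1. The rules side by side.** Section 5.2.1 and the Part 2 sentence are read as 'only if', which is their natural sense. Each DLT is taken as drug-related, with one event per participant.

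| DLTs among 3 at 1 mg | 5.2.1 | 6.2, Part 2 sentence | 6.2, second-cohort sentence | Conventional 3+3 | Halt at more than 2 patients |
|---|---|---|---|---|---|
| 0 | open 2 mg | open, if no other clinically significant related event | open | open | not met |
| 1 | do not open | do not open | **open** | treat 3 more at 1 mg | not met |
| 2 | do not open | do not open | **open** | do not open | not met |
| 3 | do not open | do not open | condition not met | do not open | met |

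The conflict sits in the rows for 1 and 2. The halt does not resolve it, because within a cohort of three it is met only at 3/3.

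**Step 2. Units.** The halt counts patients, while the second-cohort sentence counts events. One patient with three related limiting events meets neither condition.

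**Step 3. Layout.** 3 + 6 = 9 matches the planned total in 1.1 and 6.1 and leaves no room for a 1 mg expansion. 6 + 6 = 12 would match 8.6 with such an expansion, but no section describes one.

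**Step 4. Size.** The protocol states no DLT rate or escalation probability, so there is no figure to reproduce. Let p be an assumed per-participant DLT rate at 1 mg and q = 1 − p, with n = 3 and no stop after the first participant.

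- 0/3 rule: q³
- Up to two: 1 − p³
- Conventional 3+3: q³ + 3pq² × q³
- Rules conflict (1/3 or 2/3): 3pq² + 3p²q = 3pq
- Exactly 2/3: 3p²q

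At p = 0.20: q³ = 0.512; 1 − p³ = 0.992; 3+3 = 0.512 + 0.384 × 0.512 = 0.709; conflict = 3 × 0.2 × 0.8 = 0.480; exactly 2/3 = 3 × 0.04 × 0.8 = 0.096.

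| Assumed p | 2 mg opens, 0/3 | 2 mg opens, 3+3 | 2 mg opens, up to two | Conflict | Exactly 2/3 |
|---|---|---|---|---|---|
| 5% | 0.857 | 0.973 | 0.9999 | 0.143 | 0.007 |
| 10% | 0.729 | 0.906 | 0.999 | 0.270 | 0.027 |
| 20% | 0.512 | 0.709 | 0.992 | 0.480 | 0.096 |
| 33% (1/3) | 0.296 | 0.428 | 0.963 | 0.667 | 0.222 |
| 50% | 0.125 | 0.172 | 0.875 | 0.750 | 0.375 |

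If a DLT in the first participant stopped enrolment, the conflict probability would be q(1 − q²): 0.093, 0.171, 0.288, 0.370 and 0.375.

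**The case against.** The best defence is that the second-cohort sentence is a drafting slip. It directly follows the halt and reads as its complement: enrolment has not been stopped, so it continues. A halt and a separate escalation condition can coexist. The dose table in 5.2.1 and the paragraph that opens Part 2 agree with each other, and the named 3+3 method bars 2 mg after 2/3. An independent committee also reviews the first participant at each dose, and under 9.7 the DSMB may convene as required.

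Much of this stands. The sentence is an outlier, and a careful committee would probably not follow it. But it is an affirmative instruction to recruit the 2 mg cohort, and no text subordinates it. The reviews that 6.2 schedules follow the first participant at each dose, so the written rule matters most once all three 1 mg participants have been treated.

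A reader might go further and infer that the protocol has no usable escalation rule, or that the sponsor intends to escalate after 2/3 DLTs. The documents do not support either inference. Section 5.2.1 gives a clear criterion, the Part 2 sentence points the same way, and the sponsor names a method that forbids it. A reader might also infer from the higher rows of the table that the conflict is likely. Those rows rest on assumed rates of 33% and 50%, whereas 7.11.1 expects no drug-related events at these doses.

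**Conclusion.** The contradiction is established from the text and depends on no assumed rate. One sentence in 6.2 conflicts with 5.2.1 and with the next paragraph of 6.2 after 1/3 or 2/3 related DLTs, and with the named 3+3 after 2/3. It needs correcting before dosing because it governs dose doubling in the first human eyes treated by this route.

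How often it would matter is illustrative: 14%, 27% and 48% of trials at assumed rates of 5%, 10% and 20%, or 9%, 17% and 29% if a DLT in the first participant stopped enrolment. These figures assume independent participants, one event each, and every DLT related.

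**What to change.** 1. Delete the second-cohort sentence in 6.2.
2. State in identical words in 1.1, 5.2.1 and 6.2 that 2 mg opens only if 0 of 3 participants at 1 mg have a DLT within 28 days. In 6.2 this replaces the sentence that opens Part 2.
3. Choose one relatedness condition and use it for both escalation and halt. The choice matters: 2.3.3 lists transient IOP rise and haemorrhage as risks of the injection itself. If any DLT counts, such an event could close 2 mg, and p in the table becomes the any-cause rate.
4. Keep the limit of more than 2 patients solely as a study-wide halt.
5. Reconcile the 3+3 label and the 12 in 8.6 with the 3 + 6 = 9 layout. If the sponsor wants an expansion after 1/3, write it out, with no escalation after 2/3 or more.

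The cost is amendment text, and the 0/3 rule adds no participants. The downside is that 2 mg is reached less often. At assumed rates of 10% and 20%, it opens in 73% and 51% of trials under 0/3, against 91% and 71% under a conventional 3+3 and 99.9% and 99% under up to two. A written-out 3+3 recovers part of that, at up to three more participants at 1 mg. That choice is the sponsor's.

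### The protocol's three written conditions for moving from 1 mg to 2 mg disagree, and no text says which one governs

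*Protocol*

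**What the plan says.** Four pieces of Protocol text bear on the step from 1 mg to 2 mg.

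- **DLT definition (1.1 and 6.2):** "Dose-limiting toxicity is defined by intraocular inflammation, elevated IOP, reduced vision (loss of ≥ 15 letters), or haemorrhage within 28 days after injection". No item is systemic or laboratory-based, if haemorrhage is read in context as ocular.
- **Escalation rule (5.2.1):** "If no dose limiting toxicity is observed in 3 patients at this given dose level, the dose will be escalated to the following level". The next level is 2 mg/0.1 mL.
- **Two-event sentence (6.2):** "If no more than two adverse events considered to be related to the study drug occur with limiting toxicity, the second cohort will be recruited".
- **Tolerance condition (6.2, next paragraph):** "Part 2 will take in place if the 3 subjects have tolerated well the dose". Section 6.2 then explains tolerance, as general guidance, and 8.3 repeats it: "a subject will not be considered to have tolerated the dose if he experiences a clinically significant drug-related adverse event or laboratory abnormality". This covers dosing and the whole follow-up period after it, and is not confined to the eye.

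Section 1.1 also has a counted stop on the same DLT list: "Enrolment will stop if > 2 patients experience dose-limiting toxicity at any time during the study". Section 9.7 gives the DSMB its own criteria for judging continuation, which include a 30 mmHg blood pressure change and systemic illness. It does not tie those criteria to the escalation rules.

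**The concern.** A dose-escalation study needs one answer to the question of whether the next dose may be given. Here one set of 1 mg results can satisfy two of the written sentences and fail the third.

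The case that brings this out is a systemic one. The protocol itself says of this drug: "Systemic injection of Fludrocortisone acetate has serious mineral corticoid and glucocorticoid side effects such as hypertension, potassium loss, Cushingoid changes, etc". It hopes that the intravitreal route avoids these effects, and 7.11.1 expects no drug-related events at these doses. Section 2.3.3 states, however, that the drug has not been given intravitreally in humans before, and the primary endpoint counts systemic as well as local events. At stake is whether the dose is doubled after a clinically significant drug-related event such as hypokalaemia or a rise in blood pressure. The written rules should settle that before the first patient is treated.

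**Working it through.** **Design figures.** Sections 1.1 and 6.2 plan 3 patients at 1 mg and 6 at 2 mg, and 3 + 6 = 9 reproduces the size in 1.1. No power calculation exists to reproduce. Section 8.6 says up to 12, which does not affect this point.

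**Rule check.** Apply each sentence to the possible results in the three 1 mg patients. DLTs are taken to be drug-related and clinically significant, with one event per affected patient.

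| Result in the 3 patients at 1 mg | 5.2.1 | 6.2 two-event sentence | 6.2 tolerance condition |
|---|---|---|---|
| A. No DLT, no significant drug-related event | escalate | recruit | met |
| B. No DLT, at least one significant drug-related systemic or laboratory event | escalate | recruit | not met |
| C. One or two patients with a DLT | not satisfied | recruit | not met |
| D. All three with a DLT | not satisfied | not satisfied (counted stop applies) | not met |

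The three agree in rows A and D. In row B two sentences say proceed and one condition fails. In row C only the two-event sentence says proceed, and it contradicts 5.2.1 as well as the tolerance condition. Naming a 3+3 algorithm does not settle row C, because the protocol does not write out what follows one or two DLTs.

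**Time windows.** The DLT window is 28 days, while tolerance runs over all follow-up. Subjects 2 and 3 enrol only after subject 1's 28-day review. When the third subject reaches Day 28, subject 1 is therefore at about Day 28 + 28 = 56 or later. A drug-related event in subject 1 after Day 28 counts under tolerance and cannot count as a DLT.

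**How often row B arises.** Let q be the per-patient probability of a clinically significant drug-related systemic or laboratory event. The documents give no value, so q is an assumption, as is independence between patients. Given no listed DLT, the probability of at least one such event among three is 1 − (1 − q)³:

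| q | 1 − (1 − q)³ |
|---|---|
| 0.01 | 1 − 0.9703 = 0.030 |
| 0.02 | 1 − 0.9412 = 0.059 |
| 0.05 | 1 − 0.8574 = 0.143 |
| 0.10 | 1 − 0.7290 = 0.271 |
| 0.25 | 1 − 0.4219 = 0.578 |

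If listed DLTs also occur, independently, with assumed per-patient probability d, row B has probability (1 − d)³ × [1 − (1 − q)³]. At d = q = 0.10 this is 0.729 × 0.271 = 0.198.

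**How often row C arises.** One or two DLTs in three patients have probability 1 − (1 − d)³ − d³:

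- d = 0.05: 1 − 0.8574 − 0.0001 = 0.143 (0.1425 before rounding)
- d = 0.10: 1 − 0.729 − 0.001 = 0.270
- d = 0.20: 1 − 0.512 − 0.008 = 0.480

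At d = q = 0.10, rows B and C together have probability 0.198 + 0.270 = 0.468. That is how often the two-event sentence and the tolerance condition would disagree under those assumed rates.

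**The case against.** The best reply is that the sentences can be read together: 5.2.1 requires no DLT, the dedicated Part 2 sentence adds tolerance, and both must hold. For those two texts this is the natural reading, and it is probably the intent. It means that the protocol does contain a written gate for systemic events. What remains is that 5.2.1 does not mention tolerance and words its own condition as sufficient. A joint reading also cannot rescue the two-event sentence, which lets the second cohort start where 5.2.1 does not.

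A second reply is that oversight covers the gap. Section 9.7 lets the DSMB weigh blood pressure change, hospitalisation, systemic illness and any other systemic event, and convene as required. The exclusion criteria also remove hypertension and clinically significant screening laboratory values. This stands and limits the harm. However, the reviews that 6.2 and 9.7 schedule follow the first participant at a dose. Neither clearly schedules a review of the completed 1 mg cohort before the first 2 mg injection.

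A third reply is that tolerance is only guidance ("As general guidance, a subject will be considered to have tolerated a dose") and that safety is left to medical judgment. That is so, but it leaves open how much weight the condition carries against two sentences that say the study will go on.

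A reader might also infer that site and committee will reach opposite decisions. The documents do not support this, because no text gives the escalation decision to the site.

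**Conclusion.** The point holds as a disagreement among written decision rules. After a clinically significant drug-related systemic or laboratory event at 1 mg without a listed DLT, 5.2.1 and the two-event sentence proceed while the tolerance condition fails. After one or two drug-related DLTs, the two-event sentence stands alone in proceeding. One affected patient out of three is enough in either case. No text ranks the rules.

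The rule check needs no event rate. It relies only on reading haemorrhage as ocular, and if systemic bleeding were included, hypokalaemia and blood pressure rises would still be off the list. The size does depend on assumed rates: 0.03 at q = 0.01 and 0.27 at q = 0.10 for the systemic case with no listed DLT. If 7.11.1 is right that no such events occur, the systemic conflict never arises.

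Two stronger readings are tempting and should not be drawn.

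- **That the protocol has no safeguard against systemic toxicity.** It has the tolerance condition and the DSMB's discretion under 9.7.
- **That the main danger is the counted stop overlooking systemic-only events.** The stop does overlook them, since it runs on the DLT list. But once escalation requires tolerance, a single such event among the three 1 mg subjects keeps Part 2 closed, so the stop adds little. For the same reason a wider DLT list is optional.

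**What to change.** 1. In 6.2, delete the two-event sentence or align it with 5.2.1, so that escalation requires no DLT in the 3 patients.
2. In 5.2.1, state that escalation also requires the 6.2 tolerance condition for all 3 subjects. Judge it on all follow-up data available when the third 1 mg subject reaches Day 28. Do not limit it to each subject's first 28 days, because that would be narrower than the present tolerance text and would ignore later events in subject 1.

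Adding drug-related systemic or laboratory events to the DLT list in 1.1 and 6.2 is optional. The 9.7 criteria should stay matters for DSMB review and should not become automatic triggers, since they include ocular pain and any reported event, and 7.11.2 expects mild eye pain from the injection.

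The cost is an amendment to wording, with no new procedures. The Schedule of Activities already has vital signs at every visit and serum chemistry including potassium at Days 0, 7 and 28. The downside is that Part 2 may be delayed or not opened somewhat more often. Compared with following 5.2.1 alone, and with no listed DLT, it would stay closed with probability 0.03 at q = 0.01 and 0.27 at q = 0.10.
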